182 BG concentration during insulin treatment is 100-180 mg/dl. The daily basal (degludec/glargine)
183 dose will be increased by 10% if the fasting BG is between 180 and 240 mg/dl or by 20% if
184 fasting BG concentration is >240 mg/dL. The total daily insulin dose (basal and prandial insulin)
185 will be increased by 20% in patients with mean BG > 240 mg/dl. In addition, the basal insulin
186 dose will be reduced by 10% if any BG is between 70-100 mg/dl, and by 20% in patients with
187 any BG < 70 mg/dl. The total daily dose will be reduced 30-40% in the event of severe
188 hypoglycemia (BG < 40 mg/dl).

189 Several clamp studies in patients with type 1 and type 2 diabetes and observations from clinical
190 practice showed that insulin degludec quickly reaches steady state after the 2nd or 3rd day of
191 therapy, a similar period reported with other basal insulin analogs^{26,27}. Based on its steady-state
192 condition, clinical pharmacology studies show that insulin degludec has a flatter, less variable
193 and more consistent glycemic effect.

194 **Treatment randomization.** Patients will be randomized using a computer-generated
195 randomization table. Treatment randomization/assignment will be coordinated by the research
196 pharmacy. A research pharmacist at each institution will follow a computer-generated block
197 randomization table based on glucose levels (BG≤200 or BG>200) at randomization.
198

199 **TREATMENT PROTOCOL - Basal Bolus Insulin Regimen with Degludec or Glargine** 200 **Once Daily plus Aspart before Meals**

201 **Patients Treated with Insulin Prior to Admission**

- 203 • Discontinue oral antidiabetic drugs on admission.

204 Subjects treated with insulin prior to admission will receive 80% or 100 % of the total daily
205 dose (TDD) given as basal bolus regimen.

206

207 **Starting Insulin Doses:**

- 208 - **BG < 200 mg/dl give 80% of TDD***
- 209 - **BG ≥ 200 mg/dl give 100% of TDD***

210

- 211
212 • Half of TDD will be given as degludec or glargine and half as rapid-acting insulin.
213 • Degludec and glargine will be given once daily at the same time of the day
214 • Patients will receive the full-dose of degludec or glargine (even if NPO) the day of
215 surgery or diagnostic procedure(s).
216 • Aspart insulin will be given in three equally divided doses before each meal. To prevent
217 hypoglycemia, if a subject is not able to eat, aspart insulin dose will be held.

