218 *** If patient was on basal only therapy consider adding prandial dose as calculated above.**
219

220 **Insulin Naïve Patients Treated with Oral Agents or GLP1-RAs**

- 221 • Discontinue oral antidiabetic drugs on admission.
222 • Starting total daily insulin dose:
223 ▪ 0.4 U/Kg/day when randomization BG between 140-400 mg/dL
224 ▪ Reduce TDD to 0.3 units per kg in patients ≥ 70 years of age and/or with an eGFR $<$
225 60 ml/min.
226 • Half of TDD will be given as glargine or degludec and half as aspart.
227 • Degludec or glargine will be given once daily, at the same time of the day.
228 • Patients will receive the full-dose of degludec or glargine insulin (even if NPO) the day
229 of surgery or diagnostic procedure(s).
230 • Aspart insulin will be given in three equally divided doses before meals. To prevent
231 hypoglycemia, if a subject is not able to eat, the dose of aspart insulin will be held.
232

233 **Supplemental insulin.** Aspart insulin will be administered following the “supplemental or
234 correction insulin scale” protocol (Appendix 1, page 21). Supplemental doses will be given for
235 BG > 140 mg/dl before meals. At bedtime, supplemental insulin will be reserved for patients
236 with BG > 250 mg/dl.

- 237 • If a patient is able and expected to eat most of his/her meals, supplemental insulin will be
238 administered before meals and at bedtime following the “usual” dose of the insulin scale
239 protocol.
240 • If a patient is not able to eat, supplemental insulin will be administered every 6 hours
241 (Appendix 1) following the “sensitive” dose of the supplemental insulin scale protocol.
242

243 **Basal Insulin adjustment.**

- 244 • Daily basal insulin dose will be adjusted as follow:
245 ▪ If the fasting and/or pre-dinner BG is between 100 - 140 mg/dl in the absence of
246 hypoglycemia the previous day: no change
247 ▪ If the fasting and/or pre-dinner BG is between 141 - 180 mg/dl in the absence of
248 hypoglycemia: increase basal insulin by 10% every day*
249 ▪ If the fasting and/or pre-dinner BG is 181 – 299 mg/dl in the absence of
250 hypoglycemia the previous day: increase basal insulin (degludec or glargine) dose by
251 20% every day*
252 ▪ If the fasting and/or pre-dinner BG is ≥ 300 mg/dl in the absence of hypoglycemia the
253 previous day: increase basal insulin (glargine) dose by 30% every day*
254 ▪ If the fasting and pre-dinner BG is between 70 - 99 mg/dl in the absence of

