- 292 • Research staff will follow the algorithm for outpatient insulin dose adjustment according
- 293 to fasting blood glucose levels (FBG) and/or random blood glucose levels (RBG)
- 294 described below (algorithm for primary care physician).
- 295

296 **During follow up we will collect the following information:**

- 297 1. Glycemic control:
 - 298 a. Mean daily fasting and premeal blood glucose levels
 - 299 b. HBA1C at 1 and 3 months after hospital discharge
 - 300 c. Hypoglycemic events
 - 301 i. A glucose alert value of <70mg/dl.
 - 302 ii. Clinically important hypoglycemia (BG < 54 mg/dl)
 - 303 iii. Severe hypoglycemia, as defined by the ADA, which denotes severe
 - 304 cognitive impairment requiring external assistance for recovery
 - 305 d. Hyperglycemic events (BG > 240 mg/dl)
- 306
- 307 2. Diabetes treatment:
 - 308 a. Number of patients receiving insulin
 - 309 b. Insulin dosage (unit/day)
 - 310 c. Use of oral agents
 - 311 d. Protocol adherence
- 312 3. Clinical Outcome:
 - 313 a. Hospital readmissions
 - 314 b. Emergency room visits
 - 315 c. Postoperative complications
- 316
- 317 4. Management after end of study
 - 318 a. Post treatment telephone call (telephone contact 2 weeks after last clinic visit) to
 - 319 confirm appropriate number of refills and follow up with primary care physician
 - 320 b. Collect information on adverse events post treatment
- 321

322 **Primary care physicians will be provided with the following algorithm for outpatient**
323 **insulin dose adjustment according to fasting blood glucose levels (FBG) or random blood**
324 **glucose levels (RBG)**

Basal Insulin (degludec and glargine)	
If mean FBG > 180 mg/dL for the last 3 consecutive days and no hypoglycemia or no random BG (RBG) <70 mg/dL	Increase daily dose by 4 IU
If mean FBG > 140 mg/dL for the last 3 consecutive days and no hypoglycemia < or	Increase daily dose by 2 IU

no RBG <70 mg/dL	
If mean FBG between 100 – 140 mg/dL and no hypoglycemia or no RBG <70 mg/dL	No Change
If any FBG between 70 – 99 mg/dl	Decrease by 4 IU or 10% of total daily dose
If any FBG or RBG 40- 69 mg/dl	Decrease by 8 IU or 20% of total daily dose
If any FBG or RBG < 40 mg/dl	Decrease total daily dose by 30 – 40%

325
326 For patients discharged on basal bolus, prandial insulin will be adjusted according to
327 postprandial blood glucose levels (PPG) measured 2 hours after the start of the meal.
328

Prandial Insulin (rapid acting insulin)	
PPG < 180	No change

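### The ≥300 mg/dl row of the inpatient basal insulin list names glargine only: probably a drafting slip, but it sits in the operative dosing rule and should be corrected

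*Combined protocol and SAP*

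**What the plan says.** Section III.C gives two inpatient titration rules for basal insulin.

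The first is the narrative under Adjustment/Titration of daily insulin dose. It opens "The daily basal (degludec/glargine" and goes on "dose will be increased by 10% if the fasting BG is between 180 and 240 mg/dl or by 20% if" fasting glucose exceeds 240 mg/dl. It adds a 20% rise in total daily dose when mean glucose is above 240 mg/dl. It contains no 30% step.

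The second is the list headed Basal Insulin adjustment, which falls under the title "TREATMENT PROTOCOL - Basal Bolus Insulin Regimen with Degludec or Glargine". Its lead-in is generic: "Daily basal insulin dose will be adjusted as follow". The increase rows are triggered by fasting and/or pre-dinner glucose, in the absence of hypoglycemia:

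- 141-180 mg/dl: +10%, no insulin named.
- 181-299 mg/dl: "increase basal insulin (degludec or glargine) dose by" 20%.
- 300 mg/dl or more: "increase basal insulin (glargine) dose by 30% every day".

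The outpatient dose table in the same section is headed "Basal Insulin (degludec and glargine") and has no arm-specific basal row.

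**The concern.** The trial compares two basal insulins that are meant to be titrated by one algorithm. As printed, the most intensive inpatient step is assigned to only one of them. Because the preceding row names both insulins, the omission can look intended. The background text ahead of Section II even offers a motive, since it notes that degludec's long action may limit day-to-day dose changes. Treatment is open label and three sites are planned, so staff know which insulin they are titrating and could resolve the row differently from site to site.

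At stake is equal titration at the highest readings. Daily basal dose is secondary outcome 4 in Section III.B, so it would be affected directly. Mean blood glucose, the primary endpoint, would be affected only through patients who reach 300 mg/dl on treatment.

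**Working it through.** **No stated figure is in dispute.** The Aim 1 sample size (Section VI.A) was checked only to confirm that it is unaffected. With margin 18, SD 45, true difference 0, one-sided alpha 0.05 and 80% power, n = 2 × (1.645 + 0.842)² × (45/18)² = 77.3, so 78 per group; the noncentral-t power at 78 is 0.8001. For attrition of 10-14%, 78/0.90 = 86.7 (87) and 78/0.86 = 90.7 (91), which bracket the planned 90. None of these inputs depends on the row.

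**Inputs for the dose gap (Section III.C).** The list gives +30% at 300 mg/dl or more. The narrative gives +20% for fasting glucose above 240 mg/dl. The starting total daily dose for insulin-naive patients is 0.4 U/kg, or 0.3 U/kg from age 70 or with eGFR below 60 ml/min. Half is basal: 0.20 or 0.15 U/kg.

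**Formula.** After k steps, the glargine-to-degludec ratio of basal dose is (1 + g)^k / (1 + d)^k, where g and d are the step sizes in the two arms.

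| Reading | g | d | One step | Two steps |
|---|---|---|---|---|
| 1. List applied to both arms | 0.30 | 0.30 | 1.30/1.30 = 1.00 | 1.69/1.69 = 1.00 |
| 2. Narrative applied to both arms | 0.20 | 0.20 | 1.20/1.20 = 1.00 | 1.44/1.44 = 1.00 |
| 3. List read literally, no step for degludec | 0.30 | 0 | 1.30/1.00 = 1.30 | 1.69/1.00 = 1.69 |
| 4. Glargine by the list, degludec by the narrative | 0.30 | 0.20 | 1.30/1.20 = 1.083 | 1.69/1.44 = 1.174 |

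**In units per kg, stepping from the insulin-naive starting dose:**

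- Reading 3, basal 0.20: 0.20 × 0.30 = 0.060 after one step; 0.20 × 0.69 = 0.138 after two.
- Reading 3, basal 0.15: 0.15 × 0.30 = 0.045; 0.15 × 0.69 = 0.1035.
- Reading 4, basal 0.20: 0.20 × (1.30 − 1.20) = 0.020; 0.20 × (1.69 − 1.44) = 0.050.
- Reading 4, basal 0.15: 0.15 × 0.10 = 0.015; 0.15 × 0.25 = 0.0375.

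**When readings 3 and 4 apply.** Reading 3 needs a day on which the only reading calling for an increase is at or above 300 mg/dl. If the other reading falls in 141-299 mg/dl, the row for that range still covers degludec. The list does not say which row prevails, so no figure is given for such days. Reading 4 needs fasting glucose above 240 mg/dl, because the narrative's basal steps use fasting values while the list also uses pre-dinner values. With a pre-dinner value of 300 or more and fasting glucose below 180 mg/dl, the narrative's fasting rule gives degludec nothing. Its total-dose rule would then add 20% only if mean glucose exceeds 240 mg/dl. The narrative does not say whether its two rules combine.

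**The case against.** The strongest reply is that the documents already settle the meaning. The title covers both insulins and the lead-in is generic. The 100-140 and 141-180 mg/dl rows name no drug, yet plainly apply to both arms, so being named is not what brings an arm under a row. The parenthesis can be read as a loose gloss on basal insulin. Section X shows the same looseness: its in-use storage sentences name only glargine although the text covers all the study insulins. No passage gives a reason for a separate degludec step.

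This stands as the better reading, and it is why the point is minor. It does not make the row correct: the printed text omits one arm in a rule that staff dose from, and no other sentence gives degludec a 30% step.

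The reply also points to buffers common to both arms: correction aspart for pre-meal glucose above 140 mg/dl, the note to the row allowing prandial adjustment at medical discretion, and the treatment failure rule in Section IV, which removes patients with persistent readings above 280 mg/dl. These stand too, although the failure rule applies only where no treatable intercurrent cause has been found.

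A reader might go further and infer that the plan deliberately titrates the arms differently, or that the row tilts the trial toward degludec. The documents support neither. There is no stated intent. With degludec as the test insulin, a smaller degludec step would raise its mean glucose and work against showing non-inferiority. No direction can be claimed for hypoglycemia, because the plan gives neither the frequency of readings at this level nor a link from this dose step to events.

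**Conclusion.** The row is wrong as printed, most likely through a slip, and the point is minor. The gap is zero if either rule is applied to both arms. Under a literal reading of the list it is 30% of basal dose after one step and 69% after two. If degludec falls back on the narrative rule it is about 8% and 17%. It would be a mistake to treat any one of these as the gap the plan produces, since no text directs sites to use a different rule for each arm.

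The two-step figures assume qualifying readings on successive days without hypoglycemia. The per-kg figures assume steps from the insulin-naive starting dose. The share of patients reaching 300 mg/dl on treatment is not given, so the effect on the arm means of dose or glucose cannot be computed. Given the context and the buffers it is probably small, and it would not produce false non-inferiority.

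**What to change.** Insert *degludec or* before *glargine* in the row for 300 mg/dl or more, so that the 30% step names both insulins, and notify the sites. In the same notice, state that the Basal Insulin adjustment list governs in both arms. Without that sentence the narrative would still give +20% at the same fasting readings, and correcting the row alone would leave sites with two answers.

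If patients were already treated under this text, an optional check is to tabulate basal dose changes by arm after fasting or pre-dinner readings of 300 mg/dl or more. The data are already planned: daily basal dose (Section III.B, secondary outcome 4), insulin administration records (Section V, Subject Compliance), and daily fasting and pre-meal glucose (Section V, Aim 1 flow chart).

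The cost is two words, one sentence on precedence and a site memo, plus one descriptive table if the optional check is done. Sample size, power, alpha and data collection do not change.

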86 **glargine once daily plus aspart insulin before meals.** We will analyze a total of 180 subjects
87 with T2D treated prior to admission with diet, oral hypoglycemic agents, short-acting GLP1-RA
88 (except long-acting exenatide, dulaglutide and albiglutide), or insulin therapy (except degludec
89 and glargine U300) will be included in this prospective, randomized, open label trial to compare
90 the safety and efficacy of a basal bolus regimen with degludec and glargine in patients with T2D
91 admitted to general medicine and surgery services. Secondary end points include length of stay,
92 hospital complications, and hospital readmissions.

93
94 **Objective 2: To determine differences in glycemic control after hospital discharge between**
95 **treatment with degludec and glargine in medicine and surgery patients T2D.** Patients with
96 poorly controlled diabetes (HbA1c $\geq 7.0\%$) enrolled in Aim 1 will be invited to participate in this
97 open label prospective outpatient study. At hospital discharge, patients will be treated following
98 an HbA1c based algorithm²⁴ for a total duration of the outpatient follow-up of 3 months (see
99 hospital discharge algorithm, page 7).

100

101 **III. RESEARCH DESIGN AND METHODS**

102 **III.A Study Hypothesis (hypotheses):**

103 **Hypothesis #1:** Treatment with degludec and glargine will result in equivalent glycemic control
104 in general medicine and surgery patients with T2D. Degludec will result in lower number of
105 hypoglycemia compared to glargine.

106
107 **Hypothesis:** treatment with degludec and glargine will result in a similar improvement in HbA1c
108 levels after hospital discharge. Degludec will result in lower number of hypoglycemia compared
109 to glargine.

110

111 **III.B Endpoints:**

112 **The primary endpoint** of the trial is non-inferiority in mean differences between treatment groups
113 in their mean blood glucose concentrations during the first 10 days of therapy (non-inferiority
114 will be determined at a difference < 18 mg/dl). All participants who receive ≥ 2 doses of study
115 drug will be included in the analysis.

116

117 **Secondary outcomes** include differences between treatment groups in any of the following
118 measures: Endpoints 1-4 (glycemic control) will be analyzed during the first 10 days of therapy
119 and endpoints 5, 7, 8, and 9 (length of stay and complications) will be analyzed during hospital

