398 possible consequences of the study.
- 399 9. Female subjects who are pregnant or breast-feeding at time of enrollment into the study.
- 400 10. Known or suspected allergy to trial medication(s), excipients, or related products.
- 401 11. Previous participation in this trial.

402

403 **Withdrawal Criteria**

- 404 1. The subject may withdraw at will at any time.
- 405 2. The subject may be withdrawn from the trial at the discretion of the investigator due to a
406 safety concern or if judged non-compliant with trial procedures or included in contravention
407 to the inclusion and/or exclusion criteria.

- 408 3. Subject admitted to the ICU who required continuous intravenous insulin infusion to maintain
409 glycemic control.
- 410 4. Pregnancy or intention to become pregnant.
- 411 5. Treatment with oral or injectable corticosteroid (equivalent or higher than prednisone
412 5mg/day), parenteral nutrition and immunosuppressive treatment after randomization.

413 **Treatment Failure Criteria**

414 Subjects with persistent hyperglycemia (≥ 2 glucose readings ≥ 400 mg/dL, ≥ 3 consecutive
415 glucose readings > 280 mg/dL, or with a mean daily blood glucose concentration ≥ 280 mg/dL)
416 and no treatable intercurrent cause for the hyperglycemia has been identified, will be considered
417 as treatment failure and discontinued from the study. Subjects will be started on continuous
418 insulin infusion if needed.

420 **Subject Replacement**

421 There will be no replacement of subjects in this trial.

423 **V. Visit Procedures**

424 Upon arrival to the emergency department or medical or general surgical wards, subjects will be
425 screened. Patients with a known history of T2D treated with diet alone, any combination of
426 OADs, and insulin prior to admission will be considered potential candidates for this study.
427 Patients admitted with acute or chronic medical illnesses, emergency or elective surgical
428 procedures and trauma would be included in the study.

429 Patients will be treated with a basal bolus insulin regimen as previously reported. In brief,
430 subjects treated with insulin prior to admission will receive 80% of the total daily outpatient
431 insulin dose given. Insulin naïve patients will discontinue oral agents and will receive a starting
432 total daily dose (TDD) of 0.4 U/kg/day for BG between 140 mg/dl and 400 mg/dL. The starting
433 TDD will be reduced to 0.3 U/kg/day in patients ≥ 70 years or with a GFR < 60 ml/min. Both

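### Patients who meet the withdrawal or treatment-failure criteria leave the study, yet the plan does not secure their whole-stay outcomes (length of stay, complications, mortality) after that point

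*Combined protocol and SAP*

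**What the plan says.** **Removal (section IV).** Treatment Failure Criteria cover "Subjects with persistent hyperglycemia (≥ 2 glucose readings ≥ 400 mg/dL, ≥ 3 consecutive" readings above 280 mg/dL, or a mean daily glucose of at least 280 mg/dL, where no treatable intercurrent cause is found. Such patients are classed "as treatment failure and discontinued from the study". Withdrawal Criteria include item 3, "Subject admitted to the ICU who required continuous intravenous insulin infusion to maintain" glycaemic control, and item 5, "Treatment with oral or injectable corticosteroid (equivalent or higher than prednisone" 5 mg/day, together with "parenteral nutrition and immunosuppressive treatment after randomization". Under Subject Replacement: "There will be no replacement of subjects in this trial".

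**Endpoints (sections II and III.B).** Objective 1 names length of stay, hospital complications and readmissions as secondary. Section III.B sets the window: "and endpoints 5, 7, 8, and 9 (length of stay and complications) will be analyzed during hospital" stay. Those four endpoints are length of stay, cardiac complications, acute kidney injury and hospital mortality. Endpoint 6 (readmissions and emergency visits) runs to 12 weeks after discharge.

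**Analysis (sections III.B and VI).** The only stated analysis set, given with the primary endpoint, is patients with at least two doses of study drug. Section VI has no missing-data rule and no separate set for the secondary endpoints.

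**The concern.** The endpoint window and the removal rule overlap: patients can be taken out during the very stay over which their outcomes are to be compared. Nothing distinguishes coming off study insulin from leaving follow-up, and nothing says hospital outcomes are still collected afterwards.

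The loss would not be random. ICU transfer on an insulin infusion and parenteral nutrition usually mark a more complicated course, and the hyperglycaemia rule depends on glucose control, which is what the arms are compared on. The trial is also open label, and withdrawal item 2 allows removal at the investigator's discretion for a safety concern, so withdrawal could differ by arm. At stake are understated complication and mortality rates in both arms and, if withdrawals are unequal, a distorted safety comparison.

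**Working it through.** **1. The plan's own figure (VI.A).** Margin 18 mg/dl, SD 45 mg/dl, true difference 0, one-sided alpha 0.05, power 80%:

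n = 2 × (45/18)² × (1.645 + 0.842)² ≈ 77.3, so 78 per arm, as stated (exact t-test power 80.0%).

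Inflating by n/(1 − d): 78/0.90 gives 87, 78/0.87 gives 90, 78/0.86 gives 91. The planned 90 per arm fits the 10-14% attrition allowance and is not in dispute. The allowance is 180 × 0.10 = 18 to 180 × 0.14 ≈ 25 patients. Its reasons are not stated.

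**2. Does other text secure the outcomes?**
- *Adverse events (XII).* Events are collected from consent, at all following contacts, until a telephone contact two weeks after the last study visit. Death and prolonged hospitalisation are serious events, and cardiovascular events get extra data collection. Withdrawn patients are not mentioned, and their last study visit is not defined.
- *Flow charts (V).* Neither schedules a contact for a withdrawn patient. The inpatient chart has no chemistry row, although endpoint 8 needs serial creatinine. Length of stay is not an adverse event.
- *Analysis set (III.B).* The two-dose rule may keep a patient withdrawn on day 4 in the denominator, but it does not supply data from day 5 on.

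**3. Possible size (hypothetical).** The documents give no complication rates and no withdrawal rates by reason. Assume that all attrition is of this kind (w = 0.10-0.14), that the event rate is r_c = 0.10 in retained and r_w = 0.20-0.40 in withdrawn patients, and that every event in a withdrawn patient follows withdrawal.

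Share of events in withdrawn patients = w·r_w / [(1 − w)·r_c + w·r_w]
- Low: 0.10 × 0.20 / (0.90 × 0.10 + 0.10 × 0.20) = 0.020/0.110 = 18%
- High: 0.14 × 0.40 / (0.86 × 0.10 + 0.14 × 0.40) = 0.056/0.142 = 39%

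The result is sensitive to the assumptions. With r_c = 0.05, r_w = 0.10-0.40 and w = 0.05-0.14, the share runs from 0.005/0.0525 = 10% to 0.056/0.099 = 57%.

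**4. Unequal withdrawal (hypothetical).** Take 8% withdrawn in one arm and 16% in the other, with event rates of 10% retained and 30% withdrawn.
- True rates: 0.92 × 0.10 + 0.08 × 0.30 = 11.6%; 0.84 × 0.10 + 0.16 × 0.30 = 13.2%.
- Withdrawn patients dropped from the denominator: 10% and 10%.
- Withdrawn patients kept and counted event-free: 0.92 × 0.10 = 9.2%; 0.84 × 0.10 = 8.4%.

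A true excess of 1.6 points disappears in one handling and reverses in the other. The plan does not say which would apply.

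**The case against.** The strongest reply is that loss is inferred. No sentence says data collection stops; III.B states the whole-stay window without exception, and section XII requires adverse events to be collected and reported. Suppose a patient goes to the ICU on an insulin infusion on day 4, has kidney injury on day 5 and dies on day 8. The death could well be reported as a serious event. This stands: a reader might infer that these events are lost, but the documents support only that they are not secured. Kidney injury by the protocol's definition and length of stay still depend on what each site chooses to do.

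A reader might also infer that the rules single out the sickest patients. That is too strong. ICU transfer alone is not a criterion, corticosteroids or immunosuppressives need not mean deterioration, and the failure rule excludes hyperglycaemia with a treatable intercurrent cause. An infarction that prompts the transfer precedes withdrawal.

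Nor do failures go wholly uncompared. Every failure trigger requires at least one reading above 240 mg/dl, so failures after day 1 contribute to endpoint 3. Failure as such, however, is not a listed endpoint.

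Finally, this is a pilot and these endpoints are secondary and unpowered. The 1.6-point difference in step 4 is about 1.4 patients per arm of 90, against a standard error of √[(0.116 × 0.884 + 0.132 × 0.868)/90] ≈ 4.9 points. That limits the weight of the point, but it does not reconcile the two sections.

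**Conclusion.** The point holds as a conflict within the plan. Section IV takes patients out during the stay; III.B compares outcomes over the whole stay; nothing separates the end of study treatment from the end of follow-up. Followed as written, the rule permits loss related to illness course and glucose control. With equal withdrawal the main effect is understated rates and lower precision; with unequal withdrawal the comparison could be biased.

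The size and direction cannot be derived from the documents. The 18-39% figure rests on assumed event rates, on treating all 10-14% attrition as these withdrawals, and on all their events coming after withdrawal. A reader might take step 4 to show that a difference between arms would be hidden. It shows only that the answer depends on a denominator the plan leaves open. The change is worth making because data not collected at the time may be hard to recover.

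**What to change.** Reconcile section IV with III.B by separating discontinuation of study treatment from withdrawal from follow-up. The clinical criteria and treatment decisions stay as they are.

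- For every randomised patient who has not withdrawn consent for data collection, abstract endpoints 5, 7, 8 and 9 from the medical record to discharge, and endpoint 6 to 12 weeks where obtainable.
- Analyse these endpoints by randomised arm, and say so in VI.A.
- Report the number of treatment failures and withdrawals by reason and arm.

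If follow-up after withdrawal is already intended, stating it meets the first item.

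**Cost.** Protocol wording, plus extra abstraction for at most about 18-25 patients if attrition is as planned and all of this kind. Section V already uses electronic records to document insulin administration. The planned 180 does not change. One downside is that events after the switch off study insulin are included; an on-treatment analysis can be shown alongside.
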